### 8.3.5 ADVERSE EVENT REPORTING

Adverse events (AEs) and, Serious adverse events (SAEs) will be reported to IRB following its guidelines. Adverse events will be reported to the DSMB. The PI will follow the DSMB charter guidelines. The sign off on the adverse event will be done following the DSMB charter and IRB guidelines.

### 8.3.6 SERIOUS ADVERSE EVENT REPORTING

The study investigator shall complete an Unanticipated Adverse Device Effect Form and submit to the study sponsor and to the reviewing Institutional Review Board (IRB) as soon as possible, but no later than 10 working days after the investigator first learns of the effect. The study sponsor is responsible for conducting an evaluation of an unanticipated adverse device effect and shall report the results of such evaluation to the Food and Drug Administration (FDA) and to all reviewing IRBs and participating investigators within 10 working days after the sponsor first receives notice of the effect. Thereafter, the sponsor shall submit such additional reports concerning the effect as FDA requests.

### 8.3.7 REPORTING EVENTS TO PARTICIPANTS

The patients are continuously monitored by a mobile cardiac telemetry system. The insertion site will be examined to determine if there are signs of infection or electrode migration. The PI will inform the patients of the AEs and SAEs when they occur and again during the routinely scheduled follow up. The PI will coordinate with the patient's physician in managing these AEs and SAEs to ensure patient safety.

### 8.3.8 EVENTS OF SPECIAL INTEREST

We do not expect to observe events of special interest in this study.

### 8.3.9 REPORTING OF PREGNANCY

Not applicable.

## 8.4 UNANTICIPATED PROBLEMS

### 8.4.1 DEFINITION OF UNANTICIPATED PROBLEMS (UP)

The Office for Human Research Protections (OHRP) considers unanticipated problems involving risks to participants or others to include, in general, any incident, experience, or outcome that meets all of the following criteria:

- Unexpected in terms of nature, severity, or frequency given (a) the research procedures that are described in the protocol-related documents, such as the Institutional Review Board (IRB)-approved research protocol and informed consent document; and (b) the characteristics of the participant population being studied;
- Related or possibly related to participation in the research ("possibly related" means there is a reasonable possibility that the incident, experience, or outcome may have been caused by the procedures involved in the research); and
- Suggests that the research places participants or others at a greater risk of harm (including physical, psychological, economic, or social harm) than was previously known or recognized.

This definition could include an unanticipated adverse device effect, any serious adverse effect on health or safety or any life-threatening problem or death caused by, or associated with, a device, if that effect, problem, or death was not previously identified in nature, severity, or degree of incidence in the investigational plan or application (including a supplementary plan or application), or any other unanticipated serious problem associated with a device that relates to the rights, safety, or welfare of subjects (21 CFR 812.3(s)).

#### 8.4.2 UNANTICIPATED PROBLEM REPORTING

The investigator will report unanticipated problems (UPs) to the reviewing Institutional Review Board (IRB) and to the Data Coordinating Center (DCC)/lead principal investigator (PI). The UP report will include the following information:

- Protocol identifying information: protocol title and number, PI's name, and the IRB project number;
- A detailed description of the event, incident, experience, or outcome;
- An explanation of the basis for determining that the event, incident, experience, or outcome represents an UP;
- A description of any changes to the protocol or other corrective actions that have been taken or are proposed in response to the UP.

To satisfy the requirement for prompt reporting, UPs will be reported using the following timeline:

- UPs that are serious adverse events (SAEs) will be reported to the IRB and to the DCC/study sponsor within 24 hours of the investigator becoming aware of the event.
- Any other UP will be reported to the IRB and to the DCC/study sponsor as soon as possible, but no later than 10 business days of the investigator becoming aware of the problem.
- All UPs should be reported to appropriate institutional officials (as required by an institution's written reporting procedures), the supporting agency head (or designee), and the Office for Human Research Protections (OHRP) as soon as possible, but no later than 10 business days of the IRB's receipt of the report of the problem from the investigator.

An investigator shall submit to the sponsor and to the reviewing Institutional Review Board (IRB) a report of any unanticipated adverse device effect occurring during an investigation as soon as possible, but in no event later than 10 working days after the investigator first learns of the effect (21 CFR 812.150(a)(1)). A sponsor who conducts an evaluation of an unanticipated adverse device effect under 812.46(b) shall report the results of such evaluation to the Food and Drug Administration (FDA) and to all reviewing IRB's and participating investigators within 10 working days after the sponsor first receives notice of the effect. Thereafter the sponsor shall submit such additional reports concerning the effect as FDA requests (21 CFR 812.150(b)(1)).

#### 8.4.3 REPORTING UNANTICIPATED PROBLEMS TO PARTICIPANTS

The PI will inform the patients of unanticipated problems when they occur and again during the routinely scheduled follow up. The PI will coordinate with the patient's physician in managing these unanticipated problems to ensure patient safety.

## 9 STATISTICAL CONSIDERATIONS

### 9.1 STATISTICAL HYPOTHESES

*State the formal and testable null and alternative hypotheses for primary and key secondary endpoints, specifying the type of comparison (e.g., superiority, equivalence or non-inferiority, dose response) and time period for which each endpoint will be analyzed.*

- Primary Efficacy Endpoint(s):

The average AF burden.

- Secondary Efficacy Endpoint(s):

- 1) Time-dependent reduction of AF burden
- 2) Ventricular rate during AF
- 3) Average SKNA
- 4) Quality of life
- 5) Reduction of AF burden after cross over from control to experimental group

**Our primary research hypothesis is that** chronic subcutaneous nerve stimulation can control AF in patients with severe symptomatic AF unresponsive to conventional therapies.

The primary endpoint is the average of AF burden at the end of the first week. Patients who do not experience AF during the first week will have a value of 0 as AF burden. The average of AF burden at the end of the first week will be calculated per patient as the proportion of time spent in AF during the first week divided by the number of days a patient is under observation during the first week.

We will test the null hypothesis of no difference in the average AF burden between the treatment groups versus the alternative hypothesis that the average AF burden is lower in the intervention group than the sham group.

**The following pairs of secondary null and alternative hypotheses will be tested:**

- 1) that the trajectories of reduction of AF burden by time between treatment and control groups are the same versus that the trajectories are different;
- 2) that reduction of AF burden in treatment group does not depend on time versus that the reduction of AF burden is dependent on time;
- 3) that effects of ScNS and sham stimulations on ventricular rate control during AF are the same for the treatment and the control groups versus that the effects are different between the two groups;
- 4) that reduction of SKNA is the same between the treatment and the control groups versus that the reduction of SKNA is different between the two groups;
- 5) that improvement of quality of life is the same between the treatment and the control groups versus that the improvements of QoL is different between the two groups.
- 6) There is a reduction of AF burden after crossing over from control to experimental group

### 9.2 SAMPLE SIZE DETERMINATION

The AF burden is determined by the amount of time spent in AF detected by Mobile Cardiac Telemetry patch. A recent study analyzed the results of ambulatory single-lead ECG patch sensor monitoring for 11.4 days on average in 7934 men and 5359 women with paroxysmal AF. During the monitoring period, there were a total of 1,041,504 paroxysmal AF episodes. The median daily rate of paroxysmal AF was 1.21 episodes per day (interquartile range [IQR] 0.31-4.99), and the median maximum duration per individual was 7.5 hours (IQR 2.4-18.6 hours). The median burden of AF (% of time in AF relative to entire period of monitoring) was 8.9% (IQR 3.4%-25.2%). Assuming that we implant the lead and randomize patients into experimental group (stimulation) and control group (no-stimulation), we expect to see the same average AF burden among our patients. In our previous study in canine models, subcutaneous nerve stimulation reduced atrial arrhythmia burden per 48 hours from  $211.0 \pm 204.8$  s to  $134.8 \pm 165.2$  s ( $\Delta = -76.3 \pm 44.8$  s) versus a reduction of  $-5 \pm 9.5$  seconds in the sham group. Assuming the same standard deviation of the change of AF burden from baseline in the two randomized groups as 44.8 and accounting for the patient retention rate of 70%, we need 15 per arm (total 30 patients) for 80% power at 2-sided alpha 0.025 to detect an effect size of 1.59 at the end of one week between Group A (experimental) and Group B (control) using the Wilcoxon rank sum test. If the treatment suppresses AF by 75% while the sham does not suppress AF at the end of one week, we have 86% power to detect this difference at 2-sided alpha 0.025 using Fisher's exact test. We have budgeted for 32 patients to ensure that we have sufficient funds to complete the study.

### 9.3 POPULATIONS FOR ANALYSES

1. Safety set: the set of patients who have undergone surgery to insert the subcutaneous lead
2. modified intention-to-treat set: the set of patients who have either the subcutaneous nerve stimulation or the sham stimulation performed AND have baseline average AF burden AND at least the first week's post-stimulation average AF burden.

Our sensitivity analysis on the modified intention-to-treat set will be using the safety set: we will assume 0 reduction in AF burden for patients missing either the baseline or the first week post-baseline AF burden.

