### 6.3 MEASURES TO MINIMIZE BIAS: RANDOMIZATION AND BLINDING

The patient will be consented to undergo surgery. After the device implantation, the patients will be randomized to experimental and control groups using Redcap. We will attempt to blind the patients, although the tingling or pain associated with the stimulation may make blinding difficult. All data analyses performed by the co-investigators and the rhythm analyses performed by the Mobile Cardiac Telemetry system technicians will be blinded. The experimental group will receive stimulation at 3.5 mA output, while the control group will receive no stimulation. Data will be obtained during this time to determine atrial arrhythmia frequencies in both groups. The device will then be removed at the end of the second week. After the third week, we will give the option to the control group to crossover to the experimental group. This group of patients will undergo a second procedure to receive stimulation at 3.5 mA and we will follow up for another 3 weeks and 3 months post second procedure.

We will tell the patients that they will be randomized into experimental group or control group during surgery. We will attempt to blind the patients, although the tingling or pain associated with the stimulation may make blinding difficult. We will explain to all patients they may or may not feel tingling and/or pain during the 2-week stimulation time but will not tell them which group they are assigned to. All data analyses performed by the co-investigators and the rhythm analyses performed by the 7-day non-invasive monitoring system technicians will be blinded. After 3 weeks post-procedure, we will unblind the control group to give them the option of crossing over to the experimental group to receive the treatment. If they agree, these group of patients will forego the 3-month follow-up visit and will proceed with a second procedure along with follow up visits post-second procedure. Data will be obtained during this time to determine AF burden in all groups.

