## 7 STUDY INTERVENTION DISCONTINUATION AND PARTICIPANT DISCONTINUATION/WITHDRAWAL

### 7.1 DISCONTINUATION OF STUDY INTERVENTION

The study intervention is the subcutaneous nerve stimulation with an externalized neurostimulation lead. The electrical stimulation may be terminated when there are serious adverse events or when patient declines to continue with the stimulation. Discontinuation from electrical stimulation does not mean discontinuation from the study, and remaining study procedures should be completed as indicated by the study protocol. If a clinically significant finding is identified (including, but not limited to changes from baseline) after enrollment, the investigator or qualified designee will determine if any change in participant management is needed. Any new clinically relevant finding will be reported as an adverse event (AE).

The data to be collected at the time of study intervention discontinuation will include the following:

- The reasons for discontinuing the subcutaneous nerve stimulation
- The removal of the subcutaneous electrodes
- Any adverse events

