## 7.2 PARTICIPANT DISCONTINUATION/WITHDRAWAL FROM THE STUDY

Participants are free to withdraw from participation in the study at any time upon request.

An investigator may discontinue or withdraw a participant from the study for the following reasons:

- Pregnancy
- Significant study intervention non-compliance
- If any clinical adverse event (AE), laboratory abnormality, or other medical condition or situation occurs such that continued participation in the study would not be in the best interest of the participant
- Disease progression which requires discontinuation of the study intervention
- If the participant meets an exclusion criterion (either newly developed or not previously recognized) that precludes further study participation
- Participant unable to receive subcutaneous nerve stimulation after the electrode is implanted for any reason.

The reason for participant discontinuation or withdrawal from the study will be recorded on the Case Report Form (CRF) using the Redcap database. Subjects who sign the informed consent form and are randomized but do not receive the study intervention may be replaced. Subjects who sign the informed consent form, and are randomized and receive the study intervention, and subsequently withdraw, or are withdrawn or discontinued from the study, will not be replaced.

Based on the results of the canine study, reduced sympathetic nerve discharges may be associated with reduced heart rate. Therefore, we will terminate the study if the patients are found to have the following symptoms/signs which require cardiac pacemaker implantation according to the current ACC/AHA guidelines:

1. Third-degree AV block at any anatomic level associated with any one of the following conditions:
  - a. Bradycardia with symptoms presumed to be due to AV block.
  - b. Arrhythmias and other medical conditions that require drugs that result in symptomatic bradycardia.
  - c. Documented periods of asystole  $\geq 3.0$  seconds or any escape rate  $<40$  beats per minute (bpm) in awake, symptom-free patients.
2. Second-degree AV block regardless of type or site of block, with associated symptomatic bradycardia.

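### The set that evidently carries the primary analysis depends on treatment received after randomisation, and untreated randomised patients may be replaced, so exclusions can fall unevenly between the arms

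*Combined protocol and SAP*

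**What the plan says.** Section 9.4.2 names no analysis set for the primary endpoint. Section 9.3 calls the safety-set analysis a sensitivity analysis on the modified intention-to-treat (mITT) set, so the mITT set is evidently primary. Section 9.4.3 names it for the secondary endpoints. It has two conditions:

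- treatment and baseline: "the set of patients who have either the subcutaneous nerve stimulation or the sham stimulation performed AND have baseline average AF burden";
- outcome: "at least the first week's post-stimulation average AF burden".

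The safety set is "the set of patients who have undergone surgery to insert the subcutaneous lead". For the sensitivity analysis on that set, "we will assume 0 reduction in AF burden for patients missing either the baseline or the first week post-baseline AF burden".

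Section 6.3 fixes the order of events: "After the device implantation, the patients will be randomized to experimental and control groups using Redcap". Section 7.2 lists among the reasons for which an investigator may withdraw someone: "Participant unable to receive subcutaneous nerve stimulation after the electrode is implanted for any reason". It adds: "Subjects who sign the informed consent form and are randomized but do not receive the study intervention may be replaced". It also says that patients who receive the intervention and later withdraw or are withdrawn are not replaced. Section 7.1 says: "Discontinuation from electrical stimulation does not mean discontinuation from the study", and that remaining study procedures should be completed.

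Section 4.1 sets the sham output at 0 mA and says that the investigators program the device and cannot be blinded.

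**The concern.** Whether stimulation was performed is settled after allocation. Making it a condition of entry to the primary set means that the arms compared may no longer be the arms randomised. Replacement goes further, because a new patient can take the place of one already allocated.

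The condition is worded for both arms, but its effect need not be equal. Section 6.3 expects tingling or pain from stimulation. Section 2.3.1 lists discomfort and possible slowing of the heart as effects of stimulation, and names lead migration that prevents it from being given. At 0 mA there is no current to cause discomfort, to slow the heart or to fail to be delivered. An investigator who knows the arm takes the withdrawal decision. Section 7.2 does not say who decides on replacement.

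With 15 patients per arm, each exclusion is 1/15 = 6.7% of an arm. If the excluded active patients are those who would have done badly, the primary test is tilted towards stimulation.

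**Working it through.** **1. The plan's own sample size.** Inputs from 9.2: change of 76.3 s with stimulation and 5 s with sham, SD 44.8, two-sided alpha 0.025, 80% power, 70% retention, Wilcoxon rank sum test.

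- Effect size: (76.3 − 5)/44.8 = 1.59.
- Simulated power of the exact Wilcoxon test with normal data: 0.778 at 9 per arm and 0.827 at 10, so 10 evaluable patients per arm are needed.
- 10/0.70 = 14.3, rounded up to 15 per arm.

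The stated 15 per arm is reproduced and is not in dispute.

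**2. Who can leave the primary set.**

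| Patient | In mITT set? | Replaceable under 7.2? |
|---|---|---|
| Randomised, never stimulated | No | Yes |
| Started, then stopped, week-1 burden exists | Yes | No |
| Started, withdrawn before a week-1 burden exists | No | No |
| Telemetry missing, either arm | No | Only if never treated |

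Section 9.4.2 divides time in AF by the time under observation in week 1, so a partial week can give a value. No minimum observation time is stated.

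**3. Effect on the error rate.** Assumptions: 15 randomised per arm, normally distributed changes, no true effect, exact Wilcoxon test at two-sided 0.025, and k active patients removed. The documents do not give k. The favourable-tail column without replacement used 100,000 simulated trials, the one with replacement 40,000, and the others 20,000 each.

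| k | Worst k removed: favourable tail | Same, replaced: favourable tail | Worst k removed: two-sided | Same, replaced: two-sided | k at random from the worse half: two-sided | k at random: two-sided |
|---|---|---|---|---|---|---|
| 0 | 1.2% | – | 2.3% | 2.3% | 2.3% | 2.2% |
| 1 | 2.7% | 2.7% | 3.4% | 3.0% | 2.3% | 2.2% |
| 2 | 5.0% | 4.8% | 5.2% | 5.0% | 2.4% | 2.4% |
| 3 | 9.0% | 6.8% | 9.2% | 6.9% | 4.1% | 2.5% |

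Random loss of 1 to 5 active patients keeps the two-sided error between 2.1% and 2.5%. The bias therefore comes from exclusion related to outcome, not from unequal numbers. In the worst case without replacement, the spurious benefit is 0.12, 0.23 and 0.33 SD for k = 1, 2 and 3.

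**4. What dilution could cost.** Under the plan's effect of 1.59 SD, suppose k active patients show zero reduction. Keeping them gives power of 0.85 (k = 2), 0.75 (k = 3) and 0.63 (k = 4), against 0.95 with none. Dropping k active patients at random gives 0.94, 0.94 and 0.92. The first set used the asymptotic test with 5,000 runs, the second the exact test.

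**The case against.** The strongest reply is that the exposed group is small and that the plan already checks it. Lead impedance is tested at implantation (1.2, 8.1), before randomisation, so some lead failures will surface before allocation and affect both arms alike. Randomisation and programming are both scheduled on the procedure day (1.3), which leaves a short window for never being stimulated. Such patients are identified before any week-1 outcome exists, so selecting them on the worst outcome is implausible. The safety set contains every randomised patient, including those replaced.

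Much of this stands, and it rules out several stronger readings that a reader might infer:

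- *Only the 3.5 mA arm can lose patients.* The documents do not say so. Infection, allergy, site pain and missing telemetry can arise in either arm. More likely in the active arm is as far as the text goes.
- *Patients who stop for pain or bradycardia are replaced and dropped.* Section 7.2 says treated patients are not replaced, and they stay in the set if a week-1 burden exists.
- *The sensitivity analysis ignores observed telemetry.* Zero is assumed only where a burden is missing.
- *The plan expects 4 to 5 such patients per arm.* The 30% loss in 9.2 (0.30 × 15 = 4.5) covers all causes. It is not a forecast of patients unable to receive stimulation.
- *Sections 7.1 and 7.2 flatly contradict each other.* Section 7.2 is permissive, so what is shown is a need to reconcile them.

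What the reply does not remove is that the safety-set analysis is secondary and uses one fixed imputation. Section 9.3 also does not say that patients are analysed in that set as randomised, or how an implanted but unrandomised patient is handled.

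**Conclusion.** The point holds as a limited exposure that can be avoided. The evidently primary set depends on an event after randomisation, replacement is allowed, and the withdrawal decision rests with someone who knows the arm. It concerns never-stimulated patients and those withdrawn before a week-1 burden exists.

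The worst-case favourable-tail error is 2.7%, 5.0% and 9.0% for 1, 2 and 3 exclusions, against about 1.2% with none, and 6.8% at 3 if those patients are replaced. These figures assume normal data, 15 per arm, a k that the documents do not give, and exclusion of exactly the worst patients. They are upper bounds, and a reader should not take them as the expected error: with loss unrelated to outcome the error stays near nominal. The case for change is that the route to bias can be closed by wording, not that a particular bias has been shown.

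**What to change.** - In 9.3 and 9.4.2, name the primary set: all randomised patients, in the allocated arm, with baseline and any week-1 telemetry, whether or not stimulation was delivered.
- Keep replaced patients in that set.
- Report non-receipt, withdrawals and replacements by arm, with reasons.
- Reconcile 7.1 and 7.2 on whether a patient who cannot receive stimulation remains in follow-up.
- Keep the present mITT analysis and the zero-imputed safety-set analysis as sensitivity analyses, and state that the latter is by randomised arm. It still matters, because the proposed primary set omits patients with no week-1 telemetry.

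The cost is wording in 7.1, 7.2, 9.3 and 9.4.2, plus some dilution of the effect if untreated patients are included. The power figures in step 4 of the working indicate how large that could be.

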#### 9.4.2 ANALYSIS OF THE PRIMARY EFFICACY ENDPOINT(S)

The primary endpoint is the average of AF burden at the end of the first week.

We will use Mobile Cardiac Telemetry to determine AF burden before surgery (eligibility visit), for two weeks during ScNS, 3 weeks following surgery and 3 months following surgery.

The average of AF burden at the end of the first week will be calculated per patient as the time spent in AF during the first week divided by the total time a patient is under observation during the first week. Change of the average AF burden from the baseline will be computed for each patient. The change in the average AF burden will be compared between group A (experimental) and group B (control) using the Wilcoxon rank sum test at a two-sided significance level of 0.025.

*The following secondary analyses of the primary endpoint will be performed:*

- 1) We will compare the baseline AF burden and the baseline number of Apple watch-detected AF episodes between groups. The number of Apple watch-detected AF will be standardized by the number of days that a subject is under observation in the respective time period. Further we will compare reduction in AF burden from baseline at weeks 1, 2, 3 and 12 in both Group A and Group B to test the null hypothesis that there is no reduction of AF burden in the two groups and between the two groups. We will also compare the reduction in the number of Apple watch-detected AF episodes from the baseline in the period between week-3 and the end of study in both Group A and Group B to test the null hypothesis that there is no difference in detected AF episodes in the two groups and between the two groups. Linear mixed effect models will be used for the comparisons, with Group, Week and Group by Week interaction as fixed effects, and a random intercept per subject. Week will be coded first as a categorical variable, and appropriate contrasts will be set up for the temporal comparisons. If outcome variables appear to be linear in time, we may model Week as a continuous fixed effect.
- 2) We may also compute the difference-in-difference statistics for the treatment for the 4 time intervals of the treatment, baseline and t weeks 1, 2, 3 and 12.

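### Scoring every missing primary change as zero is not a reliably conservative sensitivity check: its direction depends on which arm lost patients and why

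*Combined protocol and SAP*

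**What the plan says.** Section 9.4.2 compares the change in AF burden from baseline to week 1 between the arms "using the Wilcoxon rank sum test at a two-sided significance level of 0.025". The modified intention-to-treat set in section 9.3 is a complete-case set: patients must have been stimulated (active or sham) "AND have baseline average AF burden AND at least the first week's post-stimulation average AF burden".

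The sensitivity analysis moves to the safety set, "the set of patients who have undergone surgery to insert the subcutaneous lead", and there "we will assume 0 reduction in AF burden for patients missing either the baseline or the first week post-baseline AF burden". No reason is given for the value zero, and no other value is tried. It is the only analysis of the primary endpoint labelled a sensitivity analysis. The last-value-carried-forward analysis in section 9.4.3 covers SKNA and quality of life, not AF burden.

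Section 9.2 sizes the trial "accounting for the patient retention rate of 70" per cent, without splitting the expected loss by arm, visit or reason.

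Section 9.4.2 also plans linear mixed models of AF burden at weeks 1, 2, 3 and 12, GEE as a fallback, and adjustment for baseline covariates if drop-out differs between arms.

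**The concern.** A zero looks neutral, but the test uses ranks and a fall in burden is an improvement. A zero in Group B ranks worse than any sham patient who improved, so it helps ScNS. A zero in Group A ranks better than any ScNS patient who worsened. If ScNS works, it also ranks worse than a typical treated patient. The same rule can therefore push the result either way.

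Uneven loss is plausible here. Section 6.3 expects tingling or pain from stimulation, section 2.3.3 has the lead removed for persistent pain, and section 7.2 does not replace patients who withdraw after receiving the intervention. A true sham change below zero is plausible too. Section 4.2 expects strong placebo effects, and section 5.2 excludes patients with no AF during monitoring, which invites regression to the mean.

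At stake is how the check is read. Agreement or disagreement with the primary result may mainly reflect where the losses fell. A single fixed value also cannot show how far the missing outcomes would have to move before the conclusion changed.

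**Working it through.** **Inputs.** From section 9.2: mean change -76.3 (active) and -5 (sham), "Assuming the same standard deviation of the change of AF burden from baseline in the two randomized groups as 44.8", 15 per arm, 70% retention. From section 9.4.2: Wilcoxon rank sum, two-sided 0.025. The effect and SD are canine seconds per 48 hours, used because the plan uses them.

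**The plan's own figure.** Section 9.2 claims "80% power at 2-sided alpha 0.025 to detect an effect size of 1.59". The effect size is (76.3 - 5)/44.8 = 71.3/44.8 = 1.59. Simulated exact Wilcoxon power is 78.1% with 9 completers per arm and 82.7% with 10. Then 10/0.70 = 14.3, rounded up to 15 per arm. The stated sample size is reproduced. The expected loss is 0.30 × 30 = 9 patients.

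**What a zero does to one pairwise comparison.** Take the chance that the ScNS patient shows the larger fall:

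- Both observed: Φ(1.59/√2) = 0.87.
- ScNS observed, sham set to 0: Φ(76.3/44.8) = Φ(1.70) = 0.96.
- ScNS set to 0, sham observed: Φ(-5/44.8) = Φ(-0.11) = 0.46.
- Both set to 0: a tie, 0.5.

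A missing sham patient becomes a stronger-than-average comparison for ScNS, and a missing ScNS patient becomes close to a coin toss. The filled values also have no spread and count as full patients.

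**Power under the plan's effect.** Simulation, 20,000 to 40,000 trials per scenario, normal changes, loss unrelated to outcome, tie-corrected Wilcoxon:

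| Losses, active/sham | Zero rule | Observed patients only |
|---|---|---|
| 5/5 | 63-64% | 83% |
| 7/2 | 27% | 83% |
| 2/7 | 96% | 83% |
| 5/0 | 47-48% | 90% |
| 0/5 | 99% | 90% |

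Nine losses give 27% or 96% depending only on the split.

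**False positives with no treatment effect** (two-sided, nominal 2.5%, same true change in both arms):

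| Shared true change | 5/5 | 0/5 | 2/7 |
|---|---|---|---|
| 0 | 2.0% | 2.7% | 2.7% |
| -5 (plan's sham value) | 2.1% | 2.8-2.9% | 2.8-2.9% |
| -22.4 (0.5 SD, assumed) | 1.4% | 4.7% | 4.5% |
| -44.8 (1 SD, assumed) | 0.4% | 9.8% | 8-9% |

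In the sham-heavy columns with drift, nearly all rejections favour ScNS. With 7/2 losses and the same drift, rejections favouring ScNS fall to 0.2% or 0%. One extreme departs from nominal even at -5: with all nine losses in sham, rejections favouring ScNS are about 3%, against a nominal 1.25% in that direction.

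**Loss related to outcome.** No treatment effect, no drift, and the worst Group A patients leave:

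| Worst Group A patients lost | Zero rule | Observed patients only |
|---|---|---|
| 3 of 15 | about 7% | about 9% |
| 5 of 15 | about 11% | about 18% |

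The zero rule reduces the bias of the complete-case test but does not remove it.

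**The case against.** The strongest defence is that the rule is conservative in many plausible situations. With equal losses, or more losses in Group A, and missingness unrelated to outcome, it pulls towards no difference. At the plan's own sham change of -5, rejection is 2.1% to 2.9% in the patterns tabulated. The 4.5% to 10% figures need sham-heavy loss together with a shared drift that no document quantifies. When the worst Group A patients leave, the zero rule is more sceptical than the complete-case analysis, as a sensitivity check should be. All of this stands. A reader might infer that zero-fill is anti-conservative in general, and the plan's figures do not support that.

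A reader might also infer that the plan has no other answer to missing AF burden. It has: the mixed models, GEE and covariate adjustment in section 9.4.2 bear on differential loss. They do not vary what is assumed about the missing outcomes in the primary Wilcoxon test, and covariate adjustment does not carry over directly to a rank-sum test.

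The amount of missing data may also be smaller than planned. Baseline burden should rarely be missing, because section 5.1 requires at least 7 days of monitoring. A partial week-1 recording still yields a value, because section 9.4.2 divides by observed time. Section 7.1 keeps patients in follow-up after stimulation stops. The 30% is therefore closer to a ceiling for week 1, which limits the size of the problem but does not change its direction.

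**Conclusion.** The point holds in a limited form. The zero rule is not reliably conservative, because its direction depends on which arm loses patients and why. Under the plan's own effect, nine losses give 27% power (7 active/2 sham) or 96% (2/7), against about 83% in observed patients. False-positive inflation in favour of ScNS is conditional: about 4.5-4.7% or 8-10% under sham-heavy loss with an assumed drift of 0.5 or 1 SD, and about 7% or 11% if the worst 3 or 5 Group A patients leave. With balanced loss unrelated to outcome there is none.

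These results rest on normal changes, the canine effect and SD, and assumed loss patterns. Sections 4.2 and 5.2 make the direction of drift plausible but give no size.

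A reader might go further and conclude that this analysis could overturn the trial's result. Nothing in the plan lets it override the primary test. The harm is a supportive analysis that may mislead, so this is a cheap improvement and not a flaw in the primary analysis.

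**What to change.** In section 9.3, keep the zero rule as a descriptive row and add:

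1. A pre-specified tipping-point analysis of the primary Wilcoxon comparison on all implanted, randomised patients, as randomised. Vary the assumed change for missing patients separately by arm, including worsening in Group A and improvement in Group B. Report the shifts at which p crosses 0.025. Set the grid in per cent of time in AF before unblinding.
2. A table of missing baseline and week-1 burden by arm and reason.

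Two alternatives are weaker as the main remedy. Multiple imputation from about 10 completers per arm is fragile and does not address informative loss. In the worst-leavers example, a rough single draw from observed Group A patients (not full multiple imputation) rejected 12.3% and 26.6% of the time, more than the zero rule. Giving missing Group A patients the worst observed change and missing Group B patients the best has about 0% power at the planned 30% loss, so it is better shown as one corner of the tipping-point grid than alone.

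The cost is SAP wording, some extra programming and a slightly longer report. No new data are needed.
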